## **2.4.2. Totals across Groups**

A total across all groups will be presented for the General (subject disposition, demographics, etc) part of the analysis. For the Safety parts of the analysis, a total across all GLPG0634 groups will be presented for data up to and including Week 12, and for data after Week 12 or data across the entire 24 weeks of the study a total across all groups will be presented. No totals will be presented for PD or Efficacy. Totals will only be shown on tables, but not on listings or figures.

# **3. ANALYSIS PERIODS AND ANALYSIS TIME POINTS**

## **3.1. RELATIVE NUMBER OF DAYS**

The relative day (DY) is calculated as follows:

= Visit date – reference date + 1 day, when the visit date is on or after the reference date

= Visit date – reference date, when the visit date is before the reference date.

The reference date in the study is the first study medication intake date, which by definition has DY=1. There is no DY=0.

## **3.2. ANALYSIS PERIODS FOR NON-VISIT DATA**

These analysis periods are to be used for allocation of adverse events and concomitant medications into periods.

Analysis period	Period start date	Period end date
Screening	Date of signing the initial ICF.	First study drug administration date – 1 day.
First 12 weeks	First study drug administration date.	Date of the W12 visit.
Second 12 weeks	Date of the W12 visit + 1 day.	Max ( trial termination date ; date of last dose + 30 days ).
Full 24 weeks	First study drug administration date.	Max ( trial termination date ; date of last dose + 30 days ).

The trial termination date is the date of last contact with the subject, as recorded in the eCRF.

Note that the last analysis period in case of early termination will always be ended by: *Maximum ( trial termination date ; date of last dose + 30 days)*. In case the subject rolls over to DARWIN3, the trial termination date will be used (no 30 days will be added since that would be during DARWIN3).

### 3.3. ALGORITHM OF ALLOCATING VISITS TO TIME WINDOWS

All visits (including early discontinuation visits and unscheduled visits but excluding visits without data) will be placed into time windows according to their relative day (DY) in the study, according to the following allocation table:

Time point label	Target day	Interval lower bound	Interval upper bound
Screening (3)	NA	NA	NA
Baseline (1)	NA	NA	NA
Week 1	8	2	11
Week 2	15	12	21
Week 4	29	22	42
Week 8	57	43	70
Week 12	85	71	98
Week 16	113	99	126
Week 20	141	127	154
Week 24	169	155	182
>Week 24 (2)	NA	183	+∞
Follow-up (3)	7-10 days after last visit	NA	NA

(NA = not applicable).

**Notes:**

- (1) The actual baseline reference value will be determined per parameter as the last available pre-dosing data point, so might differ from this “baseline” visit interval. There will be only one baseline time point in this study: the last nonmissing value prior to first dosing of study drug.
- (2) Visits falling really late in the study (relative day > 182; excluding the follow-up visit) will be allocated to a “>Week 24” interval, and will not be shown in tables nor figures, but will only be listed.
- (3) For the screening and follow-up visits, no time window is defined. The visit as recorded in the eCRF will be used. Follow-up visits of subjects who discontinue the study prior to the Week 12 re-randomization will be shown separately as well in the tables that present the first part of the study only. For tables that present the study as a whole, all follow-up visits will be shown.

Tables, figures and listings will present the time points, not the visits.

For ECGs, a different method will be used. See section 12.3 for the details.

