### 12.2.4. Baseline and Change from Baseline

The baseline is defined as the last sample prior to first dosing, so should normally be from the Day -1 visit. Baseline will be determined per lab test individually. It is recognized that baseline tests may thus come from more than one lab sample and not just from the “baseline visit” sample.

The change from baseline will be calculated for all post-baseline time points as:

Change from baseline at time point t = value at time point t – baseline value.

The percentage change from baseline will be calculated for all post-baseline time points as:

Percent change from baseline at time point t = 100 x (change from baseline at time point t / baseline value).

Note that the percent change from baseline will be left missing in case the baseline value is zero.

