**Table 14.3.2.5: Laboratory data up to Week 12: Treatment-emergent lab abnormalities per time point**

Frequency table of the treatment-emergent lab abnormalities per lab test category (hematology, biochemistry, endocrine, urinalysis), lab test, treatment group and time point (including the worst-case). A post-baseline abnormality is considered treatment-emergent if it differs from the baseline result. Tests without normal ranges will not be presented in this table.

Population: safety.

Table to be created for the Week 12 interim analysis as well.

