**Table 14.3.2.8: Laboratory data up to Week 12: Treatment-emergent CTCAE toxicity grades per time point**

Frequency table of the treatment-emergent lab CTCAE tox grades per lab test category (hematology, biochemistry), lab test, treatment group and time point (including worst-case). A

post-baseline grade is considered treatment-emergent if it is higher than the baseline tox grade.

Table for selected tests only.

Population: safety.

Table to be created for the Week 12 interim analysis as well.

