### **12.2.11. Tables over the whole 24 weeks period**

The same tables will be made as for the first period of the study, but with the 11 adapted treatment groups. Time points to present: screening, baseline, Week 1-2-4-8-12, last on-treatment during period 1, worst case during period 1, Weeks 16-20-24, last on-treatment during period 2, follow-up (all follow-up visits in the study), worst case during period 2, last on-treatment during the whole study, worst case during the whole study. Population: Safety.

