### 12.4.2. Baseline and Change from Baseline

The baseline value will be the last nonmissing value prior to first dosing. Baseline will be determined per vital signs parameter individually. It is recognized that baseline parameters may thus come from more than one vital signs reading and not just from the “baseline visit” reading.

The change from baseline will be calculated for all post-baseline time points as:

Change from baseline at time point t = value at time point t – baseline value.

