## **12.4.7. Tables over the whole 24 weeks period**

The same tables again, but with adapted treatment groups focusing on the subjects who used GLPG0634 during both study periods. Time points to present: screening, baseline, Week 1-2-4-8-12, last on-treatment during period 1, worst case during period 1, Weeks 16-20-24, last on-treatment during period 2, last on-treatment during the whole study, follow-up (all follow-up visits in the study), worst case during period 2, worst case during the whole study.

Population: Safety.

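### For placebo subjects switched to GLPG0634 at Week 12, period 2 laboratory emergence is judged against the pre-placebo baseline, so abnormalities carried over from placebo cannot be separated from those new on drug

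*SAP*

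**What the plan says.** The notes to SAP 3.3 set one reference for the whole study: "There will be only one baseline time point in this study: the last nonmissing value prior to first dosing of study drug". SAP 12.2.4 repeats it for laboratory data ("The baseline is defined as the last sample prior to first dosing, so should normally be from the Day -1 visit") and SAP 12.4.2 for vital signs ("The baseline value will be the last nonmissing value prior to first dosing"). SAP 12.3.3 has the equivalent rule for ECG. No section defines a Week 12 reference for subjects who move from placebo to active drug.

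Emergence is judged against that one value. For normal ranges (Table 14.3.2.5): "A post-baseline abnormality is considered treatment-emergent if it differs from the baseline result". For toxicity grades (Table 14.3.2.8): "post-baseline grade is considered treatment-emergent if it is higher than the baseline tox". The ATP III rule (Table 14.3.2.11) likewise counts only a class above the baseline class.

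SAP 12.2.11 carries these rules into the second period: "The same tables will be made as for the first period of the study, but with the 11 adapted treatment groups". Its rows include Weeks 16, 20 and 24 and "last on-treatment during period 2, follow-up (all follow-up visits in the study), worst case during period 2". Under SAP 12.2.8 the period 2 worst case is drawn from all values after Week 12, and the abnormality need not be new since Week 12. SAP 2.1.2 and 4.5.2 place switched placebo subjects in their own sequence columns, one for 100 mg q.d. and one for 50 mg b.i.d.

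For the 24-week vital-sign tables, SAP 12.4.7 describes the columns differently: "The same tables again, but with adapted treatment groups focusing on the subjects who used GLPG0634 during both study periods". SAP 12.3.7 uses nearly the same wording for ECG.

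**The concern.** These are the only subjects in the trial who pass from placebo to GLPG0634 under observation, so a reader will look at their columns to see what changes when the drug is started. A single pre-placebo reference does not answer that question. After Week 12 it mixes what happened on placebo with what happened on drug.

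Elsewhere the SAP protects against this mixing. Adverse events are shown only in the period in which they began (SAP 12.1.1). Exposure in period 1 is cut off the day before the Week 12 visit because of the switch (SAP 7.8.1). Time to response leaves period 2 out because treatments may change (SAP 8.1.1). Laboratory, ECG and vital-sign emergence has no such safeguard. SAP 4.5.3 limits the separate period 2 safety analysis to adverse events, so the 24-week tables are the only summaries of these data after the switch.

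**Working it through.** The plan gives no figure on this point. The check has two parts: the rules applied to example subjects, and an estimate of size that rests on assumptions.

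**1. Rules applied to three switched placebo subjects, one analyte, low = below the normal range**

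| Subject | Pre-placebo baseline | Week 12 (end of placebo) | Week 16 (on GLPG0634) | Period 2 flag as planned | Flag against last value before GLPG0634 |
|---|---|---|---|---|---|
| A | normal | low | low | emergent | not emergent |
| B | normal | normal | low | emergent | emergent |
| C | low | normal | low | not emergent | emergent |

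A and B produce the same period 2 entry, although only B's abnormality is new on drug. C's recurrence on drug is not counted. The same holds for toxicity grades when the recurrent grade does not exceed the baseline grade.

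The Week 12 row of the same table does not separate A from B, because rows are marginal counts. One emergent subject at Week 12 and one at Week 16 may be the same person, or one resolved case and one new case. The shift tables compare the last on-treatment and worst-case results with the original baseline, and do not cross Week 12 with period 2.

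**2. Column size**

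Inputs from Protocol 8.8.2: 85 subjects per arm and an assumed placebo ACR20 response of 20% to 40%. A 1:1 re-randomisation is my assumption.

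- Non-responders: 85 × (1 − 0.20) = 68; 85 × (1 − 0.40) = 51.
- Per switch column: 68 / 2 = 34; 51 / 2 = 25.5.

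These are upper bounds. Switching depends only on the joint-count part of ACR20, so fewer subjects fail it than fail ACR20, and dropout is ignored.

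**3. Carry-over with no drug effect (all variability inputs assumed)**

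Model: 400,000 simulated subjects per scenario, each with a subject mean plus an autocorrelated within-subject term. Visits are at Weeks 0, 12, 16, 20 and 24. The limit cuts off the lowest 5% (z = −1.645). Within-subject SD is 0.4 to 0.6 of the total SD, and the 12-week autocorrelation is 0.05 to 0.6. Results across the scenarios:

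- flagged emergent at any of Weeks 16 to 24 against the original baseline: about 2.8% to 7% of switched subjects;
- flagged and already abnormal at Week 12 (type A): about 1.1% to 1.8% of switched subjects, which is 25% to 41% of those flagged;
- abnormal at baseline, normal at Week 12 and abnormal again (type C): about 0.5% to 1.3% of switched subjects.

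Per column and analyte:

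- type A: 25.5 × 0.011 = 0.28 to 34 × 0.018 = 0.61, so about 0.3 to 0.6 subjects;
- type C: 25.5 × 0.005 = 0.13 to 34 × 0.013 = 0.44, so about 0.1 to 0.4 subjects.

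**4. Sensitivity**

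Let p be the share of switched subjects whose abnormality arose on placebo, and s the share of those that persist. Carried-over count = column size × p × s. With p = 5% and s = 30%: 25.5 × 0.05 × 0.30 = 0.38. With p = 20% and s = 80%: 34 × 0.20 × 0.80 = 5.44. The upper value needs an abnormality that is both common on placebo and lasting. Nothing in the documents supports or excludes that for a given test.

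**The case against.** Much of the case on the other side stands.

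- A reader might infer that placebo-period abnormalities will be reported under the 100 mg/day arms. They will not. SAP 2.1.2 and 4.5.2 keep switched subjects in labelled columns under those who started on placebo. For data after Week 12 or over the full 24 weeks, SAP 2.4.2 gives only a total across all groups, so the counts enter no active-drug total.
- A reader might extend the point to all period 2 safety. Adverse events go by start date. The only leak is an event with an incomplete date that could belong to either period, which SAP 12.1.1 counts in both.
- The comparison of drug with placebo that randomisation supports is the one up to Week 12 in the seven original groups, and it is untouched. Laboratory safety has no p-values.
- The information is not lost. Actual values and the grade and class frequencies by visit use no baseline. Listing 16.2.11.2 shows out-of-range values by subject and time point, and Figure 14.3.2.4 plots subjects with an emergent abnormality. What is missing is a summary count that separates A from B.
- One common baseline is a recognised descriptive choice. Replacing it in two of 11 columns would give the same row two meanings.
- A reader might take the ECG and vital-sign wording to mean that placebo switchers are left out of the 24-week tables. Exclusion is not the natural reading: both sections repeat the earlier tables on the Safety population, and SAP 2.1.2 lists the switch groups for 24-week safety. The wording is still unclear, because placebo switchers did not use GLPG0634 in both periods.

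The listings allow reconstruction subject by subject, but no planned summary does it.

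**Conclusion.** The point holds for laboratory data in the two placebo-to-GLPG0634 columns. From Week 16 on, and at the period 2 last on-treatment and worst-case rows, changes, shifts and emergence are measured from before placebo. Persisting placebo-period abnormalities cannot be told apart from new ones, and same-direction or same-grade recurrences on drug go unflagged. The same baseline rule applies to ECG and vital signs, where it must also be made clear that switchers are tabulated.

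The absolute size is small: under one carried-over subject per analyte per column in the assumed model, partly offset in the count by missed recurrences. The share of 25% to 41% is a proportion of a small flagged group and should not be read as the proportion of subjects affected. Columns are small, however. One subject is 1/34 = 2.9 to 1/25.5 = 3.9 percentage points, and the problem recurs across the laboratory panel. The figures rest on assumed variability, a 1:1 split and upper-bound column sizes. The reading of the rules rests on the SAP text alone.

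**What to change.** 1. Keep the single baseline in the main 24-week tables, so that all 11 columns stay comparable.
2. For the two placebo-switch groups only, add supportive tables of period 2 results against the last nonmissing value before the first GLPG0634 dose, normally Week 12. Cover changes, shifts and treatment-emergent abnormalities by normal range, CTCAE grade and ATP III class, and the percent changes in inhibin B and testosterone. These mirror Tables 14.3.2.15 to 14.3.2.18, 14.3.2.20, 14.3.2.21 and 14.3.2.23 to 14.3.2.25. Do the same for ECG and vital signs.
3. Select the second reference by date relative to the first GLPG0634 dose and not by visit label, because the Week 12 window in SAP 3.3 runs to Day 98 and could include a value taken after the switch.
4. Leave Tables 14.3.2.19 and 14.3.2.22 as they are; they use no baseline.
5. Reword SAP 12.3.7 and 12.4.7 to name the 11 groups of SAP 2.1.2, so that the switchers' on-drug ECG and vital signs are tabulated.

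The cost is one derived reference variable, a few two-column descriptive tables, a footnote explaining the second reference and two wording changes. No new data are needed.

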### **3.4. SELECTION OF VISITS**

It is possible that more than one visit gets allocated into the same time window. In that case, only one visit will be selected for Tables and figures. The nonselected visit(s) will only be listed and flagged as use=no.

The visit with a relative day (DY) closest to the target day will be selected. If there are multiple visits at the same distance of the scheduled visit day (meaning: equal  $ABS(DY - \text{target day})$ ), then the one latest in time is selected.

In case of an additional screening result, the last pre-baseline measurement is selected as screening value for analysis. This value (not the original screening value) was also used in the clinical center to include the subject in the study.

In case more than one parameter is measured per time point (e.g. for lab), the selection is performed per parameter and per time point, not per “sample” and per time point. Missing values are removed before the selection is made.

A missing baseline value will be imputed with the last nonmissing value of a preceding visit. This can be a screening visit or an unscheduled visit prior to the first dose of study medication; whichever comes latest. If there is no nonmissing result at such screening or unscheduled visits, then the missing baseline value remains missing.

In case the screening visit is used to impute the baseline, the visit will be duplicated in the derived dataset. The original screening visit as well as the imputed baseline will be presented in the tables. In the listings, only original screening data will be shown: the original screening visit will be shown and flagged as “reference” visit. The imputed baseline will not be shown.

In case an unscheduled visit is used to impute the baseline, the visit will be renamed to “baseline” in the derived dataset. The imputed baseline will be presented in the tables. In the listings, the original unscheduled data will be shown and flagged as “reference” visit.

## **4. HANDLING OF DATA**

### **4.1. CALCULATION OF DESCRIPTIVE STATISTICS**

For continuous parameters, descriptive statistics will be presented when  $N \geq 2$ . When  $N=1$ , the observation will not be shown in the table but only in the listing.

Descriptive statistics will include at least the following:

- the number of nonmissing data points (N)
- the arithmetic mean
- the standard error (SE)
- the median, minimum and maximum
- 95% confidence interval of the mean (only when requested).

## **4.2. CALCULATION OF PERCENTAGES**

Missing values will not be included in the denominator count when computing percentages.

Imputed missing values are no longer considered to be missing values.

## **4.3. HANDLING OF VALUES BELOW (OR ABOVE) A THRESHOLD**

### **4.3.1. Safety Data**

Values below (above) the detection limit will be imputed by the value of the detection limit itself. Listings will always present the original value.

Example: if the database contains values like “<0.04”, then for the descriptive statistics the value of the detection limit (0.04) shall be used. A value like “>1000” will be imputed by “1000”.

### **4.3.2. PK Data**

Values below the detection limit will be imputed by a zero.

### **4.3.3. PD Data**

Values below the detection limit will be imputed by half of the value of the detection limit itself. Listings will always present the original value.

## **4.4. HANDLING MISSING DATA**

### **4.4.1. Handling of Missing Date (Time) or Partially Known Date (Time)**

No imputation will be done of missing date (time) fields, nor of the missing parts of partially known date (time) fields. When needed, a worst-case selection will be made. Such worst-case selection rules are elaborated in the specific sections (e.g., AE).

### **4.4.2. Handling of missing values in scales or summary parameters**

Missing items in scales or summary parameters will be imputed to allow for the derivation of the total scale/parameter score. The appropriate imputation rules will be described in the sections where the total scores are defined.

### **4.4.3. Handling of missing values and early dropouts in the efficacy analyses during the first study period (up to Week 12)**

This is for the “efficacy chapter 2” analysis.

For binary data (e.g., ACR20), two different imputations will be done for missing visits as well as early dropouts: non-responder imputation (NRI) and LOCF, up to and including Week 12. The NRI imputation will be primary, and LOCF will be secondary.

For other data (ordinal or continuous), missing visits as well as early dropouts will be imputed using the last observation carried forward (LOCF) algorithm, up to and including Week 12.

Definitions of the imputation methods:

- LOCF (all types of parameters, from binary to continuous): to impute a missing value, the last preceding nonmissing value will be used (which could even be a baseline value).
- NRI (binary response parameters only): to impute a missing response, the subject will be assumed to be a non-responder.

For all parameters, an observed-case analysis will also be performed (i.e., without any imputation). The observed-case analysis will serve as a sensitivity analysis (to ascertain the impact of early dropouts on the results) and will basically be limited to:

- ACR20/50/70/N: descriptive at W12+W24 and inferential at W12
- EULAR remission: descriptive at W12+W24
- SDAI/CDAI: descriptive at BSL+W12+W24
- DAS28: descriptive at BSL+W12+W24 and inferential at W12
- All ACR components (VAS, joint counts, CRP, HAQ-DI): descriptive at BSL+W12+W24
- QoL (FACIT,SF-36): descriptive at BSL+W12+W24.

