## **8. DEFINITIONS OF EFFICACY TABLES, LISTINGS AND FIGURES**

Mock tables, listings and figures are provided in a separate document.

All analyses will be run on the ITT population, unless specified otherwise.

General comment on the efficacy data listings: listings will present the observed-case time points, with imputed data (for components) clearly flagged. The LOCF- or NRI-imputed time points will not be shown.

General comments on the observed-case analysis:

- Is done for efficacy tables and listings, but not for efficacy plots.
- Is done for Baseline, Week 12 and Week 24 in the descriptive statistics.
- Is done for Week 12 only in the inferential statistics.
- Is done for ITT only; not for per-protocol.

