### 8.3.2. Tables over the whole 24 weeks period

Tables will present Baseline-Weeks 1-2-4-8-12-16-20-24, unless specified otherwise.

Analysis population: ITT. LOCF and observed case (descriptive only at Baseline and Weeks 12 + 24).

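### For most continuous secondary endpoints LOCF is the only between-group analysis, and the dropout check beside it is descriptive only

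*SAP*

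**What the plan says.** SAP section 4.4.3 sets the rule for ordinal and continuous efficacy data up to Week 12: "For other data (ordinal or continuous), missing visits as well as early dropouts will be imputed using the last observation carried forward (LOCF) algorithm". The value carried is the last non-missing one, "which could even be a baseline value". Protocol section 8.8.1.3 also specifies LOCF for discontinued subjects.

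The same SAP section plans an observed-case analysis for all parameters and gives its purpose: "The observed-case analysis will serve as a sensitivity analysis (to ascertain the impact of early dropouts on the results". It then lists the scope by endpoint. Two entries include inference: "ACR20/50/70/N: descriptive at W12+W24 and inferential at W12" and "DAS28: descriptive at BSL+W12+W24 and inferential at W12". The others do not, for example "SDAI/CDAI: descriptive at BSL+W12+W24"; the entries for the ACR components and for quality of life are descriptive in the same way.

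The endpoint sections follow that list. For SDAI and CDAI, section 8.3.2 says "LOCF and observed case (descriptive only at Baseline and Weeks 12 + 24", and the ANCOVA comparison with placebo (Table 14.2.1.3.4) shows LOCF in ITT only. Sections 8.5.2, 8.6.2, 8.7.2, 8.8.2, 8.9.2 and 8.10.2 also mark the observed-case analysis as descriptive only.

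The general comments at the start of SAP section 8 are looser. Of the observed-case analysis they say "Is done for Week 12 only in the inferential statistics", which limits the time point but names no endpoint.

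**The concern.** LOCF holds a dropout at an early value while other subjects may still be improving, and the ANCOVA then treats the copied value as observed. If dropout differs by arm, so does the distortion. Unequal dropout is plausible here: protocol section 8.3.4 withdraws subjects for laboratory changes and serious infection and allows stopping for treatment failure, and these reasons need not fall equally on active and placebo arms.

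At stake are the estimated effects on disability, fatigue, quality of life and disease activity, which are secondary objectives (protocol section 7.2). For these the reader gets a LOCF least-squares mean difference with a confidence interval and a Hommel-corrected p-value, but no second estimate of the same kind to set beside it.

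**Working it through.** **1. Which imputation feeds each comparison with placebo (SAP sections 4.4.3 and 8.1 to 8.10)**

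| Continuous family | LOCF comparison | Observed-case comparison, Week 12 | Flagged for the Week 12 interim |
|---|---|---|---|
| ACR-N (8.1.2) | yes | yes | comparison table, which includes observed case |
| DAS28(CRP) (8.4.2) | yes | yes | comparison and descriptive tables |
| SDAI/CDAI scores (8.3.2) | yes | no | comparison tables only |
| Joint counts (8.5.2) | yes | no | comparison tables only |
| VAS (8.6.2) | yes | no | comparison tables only |
| HAQ-DI (8.7.2) | yes | no | comparison tables only |
| CRP (8.8.2) | yes | no | comparison and normalization tables |
| FACIT (8.9.2) | yes | no | none |
| SF-36 (8.10.2) | yes | no | none |

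Nine families less two leaves seven with LOCF as the only inferential analysis. All seven have observed-case descriptive results in the final analysis. SAP section 6.2 says the interim is meant to support dose selection for phase III. The flagged tables for SDAI/CDAI, joint counts, VAS, HAQ-DI and CRP are LOCF comparisons; the tables that would carry observed-case changes from baseline are not flagged. No MMRM, multiple imputation or tipping-point analysis appears for any continuous endpoint.

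**2. What the plan quantifies.** The only planning figures are for ACR20 power (protocol section 8.8.2). With 85 per arm, two-sided alpha 0.05/6 and an uncorrected chi-square, I obtain 89.8% (20% v 48%), 91.3% (40% v 70%), 80.9% (20% v 45%) and 78.4% (40% v 66%), against the stated 90%, 90%, 80% and 80%. They reproduce. That section gives no dropout rate and no SD for a continuous endpoint, so the inputs below are assumptions.

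**3. Direct arithmetic.** Let A and P be the true Week 12 changes (active, placebo), d_A and d_P the dropout proportions, and f the share of the full change that a dropout had reached.

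LOCF difference = A × [1 − d_A(1 − f)] − P × [1 − d_P(1 − f)]

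Assume A = −1.4 SD and P = −0.8 SD, so the true difference is −0.6 SD. With f = 0.5:

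- 10% in both arms: −1.4 × 0.95 + 0.8 × 0.95 = −0.570, 5.0% too small.
- 15% active, 5% placebo: −1.4 × 0.925 + 0.8 × 0.975 = −0.515, 14.2% too small.
- 5% active, 15% placebo: −1.4 × 0.975 + 0.8 × 0.925 = −0.625, 4.2% too large.

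If every dropout carried baseline (f = 0), the results are −0.540 (10.0% too small), −1.4 × 0.85 + 0.8 × 0.95 = −0.430 (28.3% too small) and −1.4 × 0.95 + 0.8 × 0.85 = −0.650 (8.3% too large). This is an extreme case; see the objection.

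**4. Simulation on assumed DAS28-like data.** Inputs: 85 per arm, five visits, SD 1.2, correlation 0.7, true Week 12 difference −1.20, 400 trials per pattern.

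| Dropout active/placebo | LOCF difference | Shift from −1.20 |
|---|---|---|
| 10%/10% | −1.13 to −1.14 | 5% to 6% smaller |
| 15%/5% | −1.05 to −1.08 | 10% to 12.5% smaller |
| 5%/15% | −1.21 to −1.22 | 1% to 2% larger |

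A further set of runs spanned −1.03 to −1.25, that is 0.17/1.20 = 14% smaller to 0.05/1.20 = 4% larger. A likelihood analysis under MAR gave −1.19 to −1.21 throughout, with nearly the same standard error as LOCF.

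**5. Scale.** The unadjusted standard error is √(2 × 1.2²/85) = 0.184, so the largest shift is 0.17/0.184 = 0.92 standard errors. A difference of −1.03 is still 1.03/0.184 = 5.6 standard errors from zero. Simulation error is 0.184/√400 = 0.009, so the smallest shift (0.01) is barely distinguishable from none.

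**The case against.** A reader might infer that dropout bias goes unchecked. The documents do not support that: SAP section 4.4.3 plans observed-case results for every endpoint and names them as the dropout check. Since N, mean and SE are shown (SAP section 4.1), a reader can form a crude observed-case difference. What is missing is an adjusted difference with its interval, and any use of what dropouts showed before leaving.

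A reader might also infer that observed-case inference stops at ACR and DAS28(CRP). It also covers binary SDAI and CDAI remission at Week 12 (Table 14.2.1.3.7).

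Carrying baseline forward should be rare. ITT requires some post-baseline efficacy data (SAP section 2.1.1), the early discontinuation visit repeats the efficacy assessments (protocol section 8.6.2.8), and that visit is windowed into the analysis (SAP section 3.3). Baseline is carried only when a parameter has no later value, so the f = 0 figures are a bound.

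The numbers are limited too. The simulated endpoint resembles DAS28(CRP), which already has observed-case inference. Observed case was not simulated, so nothing here shows that the planned check would fail. The shifts are modest, mostly conservative, and would not overturn an effect of the assumed size. Nearly equal standard errors also weaken the complaint that copied values count as observed.

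Finally, these endpoints are secondary, quality-of-life comparisons are labelled exploratory, and LOCF follows the protocol. All of this stands. It lowers the weight of the point but leaves the gap for seven families, and for the interim comparisons of five of them.

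**Conclusion.** The point holds as an inexpensive improvement to secondary analyses; the plan is not wrong as written. For SDAI/CDAI scores, joint counts, VAS, HAQ-DI, CRP, FACIT and SF-36, LOCF is the sole between-group inferential analysis. Its check is descriptive in the final analysis, and at the interim there is no observed-case change from baseline for those of these endpoints that are shown.

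It would be a mistake to read this as a threat to the primary result. ACR20 at Week 12 uses non-responder imputation and is supported by LOCF and observed-case inference.

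The size cannot be computed from the documents. With assumed dropout of 5% to 15% per arm, DAS28-like trajectories and dropouts who had reached about half their change, the shift is roughly 2% to 14% of the treatment difference. More loss on active shrinks the difference; sufficiently more loss on placebo inflates it. Bias here means departure from the difference had all subjects continued, and the likelihood analysis recovers that only if MAR holds.

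**What to change.** Keep LOCF as the protocol specifies. Add to the pairwise-versus-placebo tables, including their Week 12 interim versions, an MMRM on change from baseline over Weeks 1, 2, 4, 8 and 12, with treatment-by-visit, baseline-by-visit, region, previous biologics and unstructured covariance. Apply it to SDAI, CDAI, HAQ-DI, joint counts, VAS, CRP and DAS28(CRP). Ending at Week 12 keeps it clear of the treatment switches.

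FACIT and SF-36 are collected only at Baseline, Week 4, Week 12 and Week 24 or early discontinuation, so use the same model on Weeks 4 and 12, or an observed-case ANCOVA at Week 12.

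Align the general comments in SAP section 8 with section 4.4.3 by naming the endpoints that receive observed-case inference.

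The cost is SAP wording and one more model per endpoint, with no new data; protocol section 8.8.1.3 already allows further exploratory analyses. The downside is reliance on MAR. SAP section 6.3.2 shows that this version postdates the interim lock, and the SAP addendum says it was written after unblinding, so an addition made now should be labelled post hoc.
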